### **8.3 Recording of Adverse Events and Serious Adverse Events**

Recording and reporting of adverse events should be in accordance with the FDA's final "Guidance for Industry and Investigators Safety Reporting Requirements for INDs and BA/BE Studies" of December 2012.

Any AE is to be recorded in the eCRF. In order to avoid vague, ambiguous, or colloquial expressions, the AE should be recorded in standard medical terminology rather than the patient's own words. Whenever possible, the investigator should combine signs and symptoms that constitute a single diagnosis.

The existence of an AE may be concluded from a spontaneous report of the patient; from the physical examination; or from special tests e.g., laboratory assessments, where applicable, or other study-specified tests (source of AE).

The reporting period begins from the time that the patient is randomized through index hospitalization until discharge or death, whichever should occur first. Any events continuing at study exit will be followed for 30 days or to resolution, or until no improvement is expected, whichever comes first. Any SAE occurring after the reporting period must be promptly reported if a causal relationship to the investigational drug is suspected. If the patient begins a new therapy, the safety reporting period ends at the time the new treatment is started, however, death must always be reported when it occurs during the study period irrespective of intervening treatment.

Each AE is to be evaluated for duration, severity, seriousness, and causal relationship to the investigational drug. The action taken and the outcome must also be recorded.

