### 3.3.2 Secondary Endpoints

Secondary endpoints assess the effect of inhaled Ampion treatment compared to placebo on the clinical outcomes for participants with respiratory distress due to COVID-19 as follows:

Objective	Endpoint
Secondary	
Assess the effect of Ampion compared to placebo on safety	

Incidence of adverse events (AEs) and serious adverse events (SAEs) from baseline to Day 60.

Assess the effect of Ampion compared to placebo on clinical health	

Change in NEWS2 score from baseline through Day 5.

Change in NEWS2 score from baseline to hospital discharge.

Assess the effect of Ampion compared to placebo on hospital stay	

Hospital length of stay (LOS) from admission to discharge.

Assess the effect of Ampion compared to placebo on oxygen use	

Change in baseline in oxygen use, blood oxygen saturation, and oxygen flow rate from baseline through Day 5.

Assess the effect of Ampion compared to placebo on progression to respiratory failure	

Percentage of participants who progress to respiratory failure (i.e., need for mechanical ventilation, ECMO, non-invasive ventilation) by Day 28.

Assess the effect of Ampion compared to placebo on intensive care	

Percentage of participants who require Intensive Care Unit (ICU) admission by Day 28.

ICU-free days through Day 28.

ICU LOS from ICU admission to discharge.

Assess the effect of Ampion compared to placebo on all-cause mortality	

Percentage of participants with a successful outcome (life) or unsuccessful outcome (death) by Day 28.

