#### **5.1.5 Post-Treatment Follow-Up (Days 28, 60)**

The following procedures will be performed at all follow-up visits (Days 28, 60):

- Mortality
- Concomitant medications/therapies
- Hospital LOS
- ICU LOS
- Ordinal scale and NEWS2 assessments
- Aes

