#### **8.3.1 AE Follow up**

All AEs occurring during the study are to be followed up in accordance with good medical practice until they are resolved, stabilized or judged no longer clinically significant or, if a chronic condition, until fully characterized. Any AEs that are considered drug-related (possibly related, definitely related) must be followed for 30 days, or to resolution, or until no improvement is expected, whichever occurs first.

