## 8.4 Serious Adverse Event Reporting

### 8.4.1 Reporting Requirements

Unexpected serious suspected adverse reactions are subject to expedited reporting to FDA. All SAEs must be entered into the eCRF within 24 hours of first knowledge of the event by study personnel. The investigator must provide his/her assessment of the relationship to study drug at the time of the initial report. The entry of an SAE into the eCRF triggers an automatic alert to the clinical research organization (CRO) safety team. The following information must be reported:

- Protocol number
- Site and/or Investigator number
- Patient number
- Demographic data
- Brief description of the event
- Onset date and time
- Resolution date and time, if the event resolved
- Current status, if event not yet resolved
- Any concomitant treatment and medication
- Investigator's assessment of whether the SAE was related to Investigative product or not.

The CRO Safety Associate will contact the site for clarification of data entered onto the eCRF, or to obtain missing information. In the event of questions regarding SAE reporting, the site may contact the appropriate individual as in [Section 8.4.2](#).

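### Protocol 8.3 ends adverse event reporting at discharge or at an undefined new therapy, while the safety endpoint, visit schedule and SAP run adverse events to Day 60

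*Protocol*

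**What the plan says.** Protocol 8.3, the section on recording AEs and SAEs, defines the period: "The reporting period begins from the time that the patient is randomized through index hospitalization until discharge or death, whichever should occur first". It then adds a second end point: "If the patient begins a new therapy, the safety reporting period ends at the time the new treatment is started". Two exceptions follow the events further. An SAE after the period must be reported if a causal link to the drug is suspected, and "death must always be reported when it occurs during the study period irrespective of intervening treatment".

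The endpoint uses a different window. Protocol 3.3.2 gives it as "Incidence of adverse events (AEs) and serious adverse events (SAEs) from baseline to Day 60", and the synopsis, Protocol 9.4.2 and SAP 3.2 and 4 repeat it. The Schedule of Assessments marks AEs at Days 28 and 60, and Protocol 5.1.5 lists them at both follow-up visits. Protocol 9.3.1.4 and SAP 9.5 collect AEs to Day 60 and apply a discharge cut-off only to the remaining safety data.

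Other instructions to sites set no discharge limit: "Any AE is to be recorded in the eCRF" (8.3), "All AEs occurring during the study are to be followed up in accordance with good medical practice" (8.3.1) and "All SAEs must be entered into the eCRF within 24 hours of first knowledge of the event by study personnel" (8.4.1).

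**The concern.** A site can comply with one part of the protocol while under-collecting for another. The AE endpoint needs 60 days of capture in every participant, but the section that tells sites how long the AE period lasts closes it at discharge, or earlier if a new therapy starts. That term is not defined. Protocol 3.1 allows COVID-19 treatments such as remdesivir and dexamethasone as standard of care, and the text does not say whether starting one counts. Read literally, the period could close during the five treatment days.

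SAP 4.1 compares crude proportions of patients with an AE or SAE over 60 days, with no adjustment for observation time. If some sites stop at discharge, capture differs between sites. It could also differ between arms if treatment changes time to discharge, which the plan itself tests as hospital length of stay.

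How much rests on this comparison is unsettled. Safety is listed first in the secondary hierarchy (Protocol 9.4.2, SAP 4). However, SAP 4.8 says AE and SAE rates are tabulated and otherwise not analysed, and SAP 9.6 says the secondary efficacy analyses get no multiplicity adjustment.

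**Working it through.** The plan states no figure to reproduce here, so the check compares passages and adds one coverage calculation.

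**Step 1. Where each text ends the AE window.**

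| Place | End of AE window |
|---|---|
| Protocol 8.3, period definition | Discharge or death, or start of a new therapy |
| Protocol 1.1, 3.3.2, 9.4.2; SAP 3.2, 4 | Day 60 |
| Protocol 1.2 | AEs marked on Days 1-5, during hospitalization, and at Days 28 and 60 |
| Protocol 5.1.5 | AEs listed at Days 28 and 60 |
| Protocol 9.3.1.4; SAP 9.5 | Day 60 for AEs; discharge for remaining safety data only |
| SAP 4.1 | Day 60 |
| Protocol 8.3 (recording sentence), 8.3.1, 8.4.1 | No discharge limit |

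Ending at death conflicts with nothing. The conflict lies in discharge and new therapy.

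**Step 2. Does any text resolve it?** No precedence rule is given. Protocol 9.3.1.4 and SAP 9.5 treat AEs and remaining safety data separately, so a discharge cut-off for AEs contradicts them directly. Section 8.3 also points both ways: besides its unlimited recording sentence, it provides for following events that continue at study exit, and SAP 5.7 puts end of study at Day 60.

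**Step 3. What a site applying the 8.3 period could miss, by type of event.**

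- Deaths: still reported under the death clause. Mortality is also collected at Days 28 and 60 (5.1.5).
- SAEs suspected to be drug-related: still reported under the exception in 8.3.
- Non-fatal SAEs judged unrelated: outside the 8.3 period. They are possibly still captured, because 8.4.1 asks for all SAEs.
- Non-serious AEs: outside the 8.3 period, with no exception.

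The last two count towards SAP 4.1, which takes any AE or SAE whatever its relatedness.

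**Step 4. Coverage, as illustration.** The inputs are the AP-014 mean hospital stays in Protocol 2.3 (27 subjects to date), 7 days on Ampion and 11 days on standard of care, and the 60-day endpoint window.

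Coverage = mean stay / 60.

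- Ampion: 7/60 = 11.7%, leaving 60 - 7 = 53 days uncovered.
- Standard of care: 11/60 = 18.3%, leaving 60 - 11 = 49 days uncovered.

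These are upper values given those stays. A hospital stay counts from admission, whereas the 8.3 period starts at randomization, and a new-therapy cut-off could only shorten it.

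**Step 5. Starting point.** Section 8.3 starts at randomization. The endpoint and 9.3.1.4 start at baseline, and the sequence in the synopsis and Protocol 3.1 puts baseline procedures before randomization. SAP 4.1 uses both. Any rewording of 8.3 has to settle this too.

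**The case against.** One defence is that *reporting* in 8.3 means expedited safety reporting, not data collection. The text does not bear this out. The section is about recording, includes a rule on eCRF entry, and draws no line between collecting and reporting. SAE reporting has its own section, 8.4.

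A better defence is that sites work from the visit schedule. AEs are scheduled at Days 28 and 60, and several sentences set no discharge limit, so a site would have to disregard planned assessments for events to be lost. This stands in part: it makes widespread loss less likely, and sites that follow the schedule lose nothing. It does not remove the conflict, because a site that follows the period in 8.3 is also following the protocol.

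The exceptions for deaths and suspected-related SAEs also stand. They narrow the gap to the event types in Step 3.

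A reader might go further and infer that the AE comparison has an inflated false-positive rate, or that it is biased between arms. The documents do not support either. They give no AE hazard, no course of that hazard after treatment, and no indication of how many sites would apply 8.3. Any rejection rate would reflect assumed values, and the plausible range includes no inflation. If time to discharge is equal between arms, the cut-off causes no bias between them. A model that treats every event after discharge as lost would also ignore the exceptions in 8.3.

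**Conclusion.** The contradiction is real, and the documents do not resolve it. Protocol 8.3 ends the AE period at discharge or at an undefined new therapy, and every other text that states an AE window ends it at Day 60. The possible loss is limited to non-serious AEs, and perhaps unrelated non-fatal SAEs, at sites that apply 8.3. It would matter between arms only if treatment also changes time to discharge.

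The only size offered is the coverage of at most about 12% and 18% of the 60 days. It assumes that the Phase I mean stays carry over to this trial. The point should be corrected on the strength of the contradiction alone, and that does not depend on the coverage figures.

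**What to change.** Reconcile 8.3 with the Day 60 window used elsewhere by stating a single AE window:

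- Record all AEs and SAEs in every participant from baseline to Day 60 or death, regardless of discharge or the start of any other therapy. If randomization is preferred as the start, change the endpoint wording and 9.3.1.4 to match.
- Delete the new-therapy cut-off.
- Keep the death clause, the reporting of suspected drug-related SAEs after the period, and the 30-day follow-up of events continuing at study exit.

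The change is wording in Protocol 8.3, plus the endpoint text and 9.3.1.4 if the start is moved to randomization. No visit is added, because the Day 28 and Day 60 calls already include AEs. The downside is somewhat more AE entries to record and process from those calls. The separate question of whether the AE comparison is a formal test in the hierarchy (SAP 4 against SAP 4.8 and 9.6) is not settled by this change.

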#### **8.3.1 AE Follow up**

All AEs occurring during the study are to be followed up in accordance with good medical practice until they are resolved, stabilized or judged no longer clinically significant or, if a chronic condition, until fully characterized. Any AEs that are considered drug-related (possibly related, definitely related) must be followed for 30 days, or to resolution, or until no improvement is expected, whichever occurs first.

#### **8.3.2 Overdose**

No information on treatment of overdose of Ampion is currently available. In the case of overdose the patient should be followed as for an AE and appropriate supportive medical treatment instigated.

## 8.4 Serious Adverse Event Reporting

### 8.4.1 Reporting Requirements

Unexpected serious suspected adverse reactions are subject to expedited reporting to FDA. All SAEs must be entered into the eCRF within 24 hours of first knowledge of the event by study personnel. The investigator must provide his/her assessment of the relationship to study drug at the time of the initial report. The entry of an SAE into the eCRF triggers an automatic alert to the clinical research organization (CRO) safety team. The following information must be reported:

- Protocol number
- Site and/or Investigator number
- Patient number
- Demographic data
- Brief description of the event
- Onset date and time
- Resolution date and time, if the event resolved
- Current status, if event not yet resolved
- Any concomitant treatment and medication
- Investigator's assessment of whether the SAE was related to Investigative product or not.

The CRO Safety Associate will contact the site for clarification of data entered onto the eCRF, or to obtain missing information. In the event of questions regarding SAE reporting, the site may contact the appropriate individual as in [Section 8.4.2](#).

### 8.4.2 SAE Contact Information

Ampio Pharmaceuticals Inc, or their designee CRO, is responsible for submitting reports of AEs associated with the use of the drug that are both serious and unexpected to FDA according to 21 CFR 312.32 and the final guidance (2012). All investigators participating in ongoing clinical studies with the study medication will receive copies of these reports for prompt submission to their Institutional Review Board (IRB) or Ethics committee (EC).

## 9 STATISTICAL METHODS

### 9.1 General Considerations

This section describes the rules and conventions to be used in the presentation and analysis of the data. The details of all these analyses will be presented in the Statistical Analysis Plan.

This trial is designed for approximately 200 patients across two treatment arms (active or control), with a 100 subjects per arm, randomized 1:1 using a random allocation sequence equally stratified by COVID-19 disease severity.

The number of participants is selected based on the effects observed for the primary endpoint, all-cause mortality. A study in the New England Journal of Medicine with over 4,000 patients receiving the standard of care (SOC) for COVID-19 found a 26% mortality rate at Day 28 (NEJM, 384;8, February 25, 2021). There was a similar observation in the Ampion Phase I study (AP-014) for patients with respiratory distress due to COVID-19 with a mortality for the SOC control arm of 21% by Day 28. In the AP-014 study, a lower mortality rate (8%) was observed for subjects receiving inhaled Ampion. Assuming the same proportions of deaths (8% for Ampion and 26% for control) by Day 28, the number of subjects (n=200) achieves at least an 80% power.

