## 1 PROTOCOL SUMMARY

### 1.1 Protocol Synopsis

Sponsor: Ampio Pharmaceuticals, Inc.	Investigational Product: Ampion™						
Title of Study:  A Randomized, Double-Blinded, Placebo-Controlled Phase II Study to Evaluate the Safety and Efficacy of Inhaled Ampion in Adults with Respiratory Distress due to COVID-19							
Rationale:  The severe acute respiratory syndrome coronavirus 2 (SARS-CoV-2) has resulted in the pandemic spread of coronavirus disease 2019 (COVID-19), which has a high rate of infection, has a high rate of hospitalization, has overwhelmed healthcare systems, and can be fatal.  Ampion is the low molecular weight filtrate of human serum albumin with the in vitro ability to modulate inflammatory cytokine levels. Ampion has the potential to improve clinical outcomes for COVID-19 patients by reducing inflammatory cytokines correlated with the disease and respiratory complications, such as Acute Lung Injury (ALI) and Acute Respiratory Distress Syndrome (ARDS).  This study aims to evaluate the effects of Ampion on mortality and clinical outcomes in patients with respiratory distress due to COVID-19. The data from this study will inform decisions for the clinical development of Ampion.							
Number of Sites:  Approximately 20 sites							
Indication:  Adults with respiratory distress due to COVID-19							
Number of Participants:  Sample size is approximately 100 participants per treatment arm							
Treatment Groups:  There are two planned treatment arms randomized 1:1, active to control:  

Treatment Arm	Investigational Treatment	

Active	Ampion for 5-days	

Control	Placebo for 5-days	

		Treatment Arm	Investigational Treatment	Active	Ampion for 5-days	Control	Placebo for 5-days
Treatment Arm	Investigational Treatment						
Active	Ampion for 5-days						
Control	Placebo for 5-days						

Sponsor: Ampio Pharmaceuticals, Inc.	Investigational Product: Ampion™
Objectives and Endpoints:	
Objective	Endpoint
Primary	
Assess the effect of Ampion compared to placebo on clinical improvement	

Change in ordinal scale from baseline through Day 5.

Change in ordinal scale from baseline through Day 28.

Secondary	

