## 3.3 Study Endpoints

### 3.3.1 Primary Endpoint

The primary endpoint assesses the effect of Ampion compared to placebo on clinical improvement. Clinical improvement is measured as the change in ordinal scale from baseline through Day 5 and Day 28.

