### Mortality

All-cause mortality will be recorded at hospital discharge, Days 28 and 60, as applicable. Cause of mortality will be assessed and documented. All-cause mortality is calculated for the primary endpoint as the percentage of participants with a successful outcome (life) or unsuccessful outcome (death).

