## 9.4 Study Endpoints

### 9.4.1 Primary Endpoint

The primary endpoint assesses the effect of Ampion compared to placebo on clinical improvement. Clinical improvement is measured as the change in ordinal scale from baseline through Day 5 and Day 28.

Let  $\mu_A$  and  $\mu_S$  represent the mean changes in the ordinal scale for Ampion and control respectively. Then, it is desired to demonstrate that the mean change for Ampion is different than the corresponding mean change for the control, respectively. Formally, this is presented as:

$$H_0: \mu_A = \mu_S \quad \text{versus} \quad H_A: \mu_A \neq \mu_S$$

The difference between Ampion and Placebo with respect to the change from baseline at Day 5 and Day 28 will be tested utilizing a Wilcoxon rank-sum test. To assess any potential time trends, an exploratory repeated measures analysis of variance will be performed with terms for treatment, time, and the interaction between the two.

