### 9.4.2 Secondary Endpoints

Secondary endpoints assess the effect of inhaled Ampion treatment compared to placebo on the clinical outcomes for participants with respiratory distress due to COVID-19. The secondary endpoints will be tested in a hierarchical manner in the order presented, and thus no adjustment to the alpha level is necessary:

Objective	Endpoint
Secondary	
Assess the effect of Ampion compared to placebo on safety	

Incidence of adverse events (AEs) and serious adverse events (SAEs) from baseline to Day 60.

Assess the effect of Ampion compared to placebo on clinical health	

Change in NEWS2 score from baseline through Day 5.

Change in NEWS2 score from baseline to hospital discharge.

Objective	Endpoint
Assess the effect of Ampion compared to placebo on hospital stay	
 
Hospital length of stay (LOS) from admission to discharge.
 

Assess the effect of Ampion compared to placebo on oxygen use	
 
Change from baseline in oxygen use, blood oxygen saturation, and oxygen flow rate from baseline through Day 5.
 

Assess the effect of Ampion compared to placebo on progression to respiratory failure	
 
Percentage of participants who progress to respiratory failure (i.e., need for mechanical ventilation, ECMO, non-invasive ventilation) by Day 28.
 

Assess the effect of Ampion compared to placebo on intensive care	
 
Percentage of participants who require Intensive Care Unit (ICU) admission by Day 28.
 
ICU-free days through Day 28.
 
ICU LOS from ICU admission to discharge.
 

Assess the effect of Ampion compared to placebo on all-cause mortality	
 
Percentage of participants with a successful outcome (life) or unsuccessful outcome (death) by Day 28.
 

The efficacy endpoints will be evaluated to estimate the treatment effect and use descriptive statistics including mean, standard deviation, percentages, minimum/maximum, and 95% confidence intervals. All endpoints will be tabulated and presented by treatment arm, cohort (moderate and severe), and timepoint. Where appropriate, data will be tabulated and presented cumulatively across cohorts and/or timepoints.

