4. HYPOTHESES

The primary endpoint assesses the effect of Ampion compared to placebo on clinical improvement. Clinical improvement is measured as the change in ordinal scale from baseline through Day 5 and Day 28.

Let μ_A and μ_S represent the mean changes in the ordinal scale for the three time points for Ampion and control respectively. Then it is desired to demonstrate that the mean change for Ampion is different than the corresponding mean change for the control, respectively. Formally, this is presented as:

$$H_0: \mu_A = \mu_S \text{ versus } H_A: \mu_A \neq \mu_S$$

The difference between Ampion and Placebo with respect to the change from baseline through Day 5 and Day 28 will be tested utilizing a Wilcoxon rank-sum test via PROC NPAR1WAY. To assess any potential time trends, an exploratory repeated measures analysis of variance will be performed with terms for treatment, time, and the interaction between the two. This will be done utilizing PROC GLM with the REPEATED option.

Secondary endpoints assess the effect of inhaled Ampion treatment compared to placebo on the clinical outcomes for participants with respiratory distress due to COVID-19. The secondary endpoints will be tested in a hierarchical manner in the order presented, and thus no adjustment to the alpha level is necessary:

Objective	Endpoint
Secondary	
Assess the effect of Ampion compared to placebo on safety	
Incidence of adverse events (AEs) and serious adverse events (SAEs) from baseline to Day 60.
Assess the effect of Ampion compared to placebo on clinical health	
Change in NEWS2 score from baseline through Day 5.Change in NEWS2 score from baseline to hospital discharge.
Assess the effect of Ampion compared to placebo on hospital stay	
Hospital length of stay (LOS) from admission to discharge.
Assess the effect of Ampion compared to placebo on oxygen use	Change in baseline in oxygen use, blood oxygen saturation, and oxygen flow rate from baseline through Day 5.
Assess the effect of Ampion compared to placebo on progression to respiratory failure	Percentage of participants who progress to respiratory failure (i.e., need for mechanical ventilation, ECMO, non-invasive ventilation) by Day 28.

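### The sample size and its only power statement rest on mortality, labelled the primary endpoint, but the primary endpoint is ordinal-scale change at Day 5 and Day 28, for which no effect, power or combination rule is stated

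*Protocol*

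**What the plan says.** **Sample-size text.** Protocol 4.1, Protocol 9.1 and SAP 2.4 share one justification: "The number of participants is selected based on the effects observed for the primary endpoint, all-cause mortality". All three assume deaths by Day 28 of 8% on Ampion and 26% on control. Protocol 9.1 concludes that "the number of subjects (n=200) achieves at least an 80% power". Protocol 5.2, under Mortality, repeats the label: "All-cause mortality is calculated for the primary endpoint as the percentage of participants".

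**Endpoint text.** The synopsis lists two primary endpoints, ordinal change through Day 5 and "Change in ordinal scale from baseline through Day 28". Protocol 3.3.1 and SAP 3.1 agree: "Clinical improvement is measured as the change in ordinal scale from baseline through Day 5 and Day 28". Protocol 9.4.1 says the "change from baseline at Day 5 and Day 28 will be tested utilizing a Wilcoxon rank-sum test". SAP 4 says the "change from baseline through Day 5 and Day 28 will be tested utilizing a Wilcoxon rank-sum test via PROC NPAR1WAY".

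**Place of mortality.** Protocol 9.4.2 and SAP 4 list Day 28 mortality last among the secondary endpoints, and "The secondary endpoints will be tested in a hierarchical manner in the order presented".

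**What is given for the primary test.** The documents state two-sided hypotheses, the Wilcoxon test, and alpha of 0.001 at the interim and 0.047 at the final analysis (Protocol 9.2.3, SAP 7.1). Those interim sections also let the sponsor change the sample size if assumptions about clinical improvement fail.

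**The concern.** The two sets of passages name different primary endpoints, and both sets are current text. The mortality calculation is the only power figure in either document, so a reader who takes the label at face value will believe the Wilcoxon analysis has at least 80% power. Nothing in the documents supports that belief.

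Two further gaps follow.

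- Power for the primary analysis is not yet a defined quantity. The plan does not say whether success needs Day 5, Day 28, either or both, or what alpha each test receives. SAP 4 adds to this by defining the mean changes over three time points while naming two.
- The interim can alter the sample size against a clinical-improvement assumption that has no stated value. The people making the unblinded recommendation would have nothing to compare the data with.

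**Working it through.** **1. Reproduce the plan's figure.** Inputs from Protocol 9.1: p1 = 0.08, p2 = 0.26, n = 100 per arm. The final alpha of 0.047 is from Protocol 9.2.3; 0.05 is shown for comparison. The test is two-sided.

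Power = Φ{ [ |p1 − p2|·√n − z·√(2p̄(1 − p̄)) ] / √(p1(1 − p1) + p2(1 − p2)) }

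- p̄ = (0.08 + 0.26)/2 = 0.17, and √(2 × 0.17 × 0.83) = 0.5312
- √(0.0736 + 0.1924) = 0.5158
- alpha 0.05, z = 1.9600: (1.8 − 1.0412)/0.5158 = 1.471, power **92.9%**
- alpha 0.047, z = 1.9863: (1.8 − 1.0552)/0.5158 = 1.444, power **92.6%**

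Exact enumeration of Fisher's test gives 91.5% and 90.9%. At least 80% therefore holds as a lower bound for a mortality test taken alone. It ignores the steps that come before mortality in the hierarchy.

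**2. Try the same for the primary test.** A Wilcoxon calculation needs the category distribution in each arm, or at least the probability that a patient on one arm has a better change than a patient on the other. Neither document gives either, so no figure can be reproduced or corrected.

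To show how open the answer is, take assumed standardized differences d on a normal shift at one time point, ignoring ties. With p = Φ(d/√2) and N = 200, Noether's formula gives power = Φ(√(12 × ¼ × 200)·(p − ½) − 1.9863).

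| Assumed d | p | Power at 0.047 |
|---|---|---|
| 0.2 | 0.556 | 27% |
| 0.3 | 0.584 | 53% |
| 0.4 | 0.611 | 77% |
| 0.5 | 0.638 | 92% |

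These effects are assumptions, not estimates from the documents.

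**3. Show why the combination rule matters.** Suppose each time point alone had 80% power at 0.047. Its test statistic then has mean 1.9863 + 0.8416 = 2.8279. Treat the two statistics as bivariate normal with an assumed correlation r, and consider the final analysis alone.

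- *Both must succeed.* At r = 0 power is 0.8 × 0.8 = 64%. At r = 1 it is 80%. The range for non-negatively correlated tests is **64% to 80%**.
- *Either suffices, 0.047 each.* At r = 0 the type I error is 1 − (1 − 0.047)² = 9.2%. At r = 0.9 it is 6.6%.
- *Either suffices, 0.0235 each.* The critical value is 2.2652, so each test has power Φ(2.8279 − 2.2652) = 71.3%. The chance that at least one succeeds is 2 × 0.713 minus the chance that both do:

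| r | Power of the either rule at 0.0235 each |
|---|---|
| 0 | 91.8% |
| 0.5 | 85.3% |
| 0.8 | 80.0% |
| 0.9 | 77.4% |

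The same data and the same 200 patients thus give materially different success probabilities, and in one case an inflated type I error, depending on a rule the plan leaves open.

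**The case against.** The best defence is that nothing is hidden. This is a Phase II trial meant to inform development. The sample-size text says plainly that deaths drive the calculation. Protocol 3.2.1 discloses that ventilation and death have become less frequent and rests the clinical-improvement objective on that. Protocol 9.2.3 plans a review of the sample size because published rates may shift. A wrong label in the sample-size section biases no estimate and changes no type I error. All of this stands, and it limits the point to a missing justification and an open decision rule.

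It does not remove the point. The plan makes a formal power claim and tests at a controlled alpha, so the claim should attach to the test that decides the trial. The interim review cannot repair the gap, because it relies on the assumption that is missing.

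Some stronger readings are tempting, but the documents do not support them.

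- *The 80% claim is false.* It is true for mortality on its own inputs.
- *The trial is underpowered for its primary endpoint.* The documents lack the inputs needed to show this either way. The AP-014 percentages of stable or improved patients in Protocol 2.3 cannot fill the gap: they are preliminary results from 27 subjects, they are a dichotomy, and the scale is not identified as the WHO one.
- *The primary test is unspecified.* Hypotheses, test and overall alpha are all given. What is missing is how the two time points combine.
- *Splitting alpha must cost power.* Each component test loses power, but in the illustration the either rule stays above 80% until the correlation reaches about 0.8.

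**Conclusion.** The inconsistency is real and should be corrected. The only stated power belongs to the last secondary endpoint, and the primary analysis has no stated sample-size basis. For mortality the figure is 92.6% by the normal approximation or 90.9% by Fisher's test at alpha 0.047, and it describes a stand-alone test.

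The size of the consequence for the primary endpoint is unknown. The step 2 and step 3 figures are illustrations. They rest on assumed effects, an assumed 80% power per time point and assumed correlations, and they show sensitivity rather than a shortfall.

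**What to change.** - **Protocol 4.1, Protocol 9.1 and SAP 2.4:** present the mortality calculation as the stand-alone power for a secondary endpoint, and say that it does not allow for the earlier steps of the hierarchy.
- **Protocol 5.2, Mortality:** delete the words that tie mortality to the primary endpoint.
- **Protocol 9.4.1 and SAP 4:** state whether success needs either time point, both, or an ordered sequence, and the alpha for each test. Bring SAP 4's reference to three time points into line.
- **Power for the primary analysis:** give the Wilcoxon power that 200 patients provide under that rule, with the assumed category distribution and effect.
- **Protocol 9.2.3 and SAP 7.1:** name that assumption as the one the interim checks.

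The cost is wording in eight sections, one decision rule and one power calculation. The correction itself needs no extra patients. The downside is that the power reported for the primary endpoint may be less favourable than the mortality figure.
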